8.3. Immunogenicity Analyses

Levels of serum anti-HPV-16 and anti-HPV-18 antibody concentrations and Interferon-γ ELISpot response magnitudes will be assessed from sera and PBMCs isolated from whole blood, respectively, collected at baseline, Week 15, and Week 36 visits. Flow Cytometry response magnitudes will be assessed from PBMCs isolated from whole blood collected at baseline and Week 15 visits.

All of the endpoints will be summarized as continuous variables at each visit. Increases from baseline for each post baseline visit from ELISpot and Flow Cytometry, and titers for each post baseline visit from ELISA will be compared between treatment arms. These comparisons will be analyzed with difference in medians and associated exact non-parametric 95% CIs.

The mITT population with at least one immunogenicity measurement will be used for these immunogenicity analyses.

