2.2. Secondary Objective

The secondary objectives of this study are:

- 1. Evaluate the safety and tolerability of VGX-3100 delivered intramuscularly (IM) followed by Electroporation (EP) with CELLECTRATM 5PSP
- 2. Determine VGX-3100 efficacy compared to placebo as measured by histopathologic regression of cervical HSIL
- 3. Determine VGX-3100 efficacy compared to placebo as measured by virologic clearance of HPV-16 and/or HPV-18
- 4. Determine VGX-3100 efficacy compared to placebo as measured by complete histopathologic regression of cervical HSIL to normal
- 5. Determine VGX-3100 efficacy compared to placebo as measured by both complete histopathologic regression of cervical HSIL to normal and virologic clearance of HPV-16 and/or HPV-18
- 6. Determine VGX-3100 efficacy compared to placebo as measured by histopathologic non-progression
- 7. Describe the clearance of HPV-16 and/or HPV-18 infection from non-cervical anatomic locations
- 8. Determine the humoral and cellular immune response following administration of VGX-3100 compared with placebo at post dose 3 and Week 36 visits as assessed relative to baseline

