3.2.2. Secondary Endpoints

The secondary endpoints of this study are:

- 1. a. Incidence and severity of local and systemic events for 7 and 28 days following each investigational treatment and for the duration of the study (through Week 88 visit)
 - b. Incidence and severity of all adverse events including SAEs, SUSAR, UADE and other unexpected AEs for the duration of the study (through Week 88 visit)
- 2. Proportion of subjects with no evidence of cervical HSIL on histology (i.e. biopsies or excisional treatment) at Week 36 visit
- 3. Proportion of subjects with no evidence of HPV-16 and/or HPV-18 in cervical samples by type specific HPV testing at Week 36 visit
- 4. Proportion of subjects with no evidence of Low grade squamous intraepithelial lesion (LSIL) or HSIL (i.e. no evidence of CIN1, CIN2 or CIN3) on histology (i.e. biopsies or excisional treatment) at Week 36 visit

- 5. Proportion of subjects with no evidence of LSIL or HSIL (i.e. no evidence of CIN1, CIN2 or CIN3 on biopsies or excisional treatment) on histology (i.e. biopsies or excisional treatment) and no evidence of HPV-16 and/or HPV-18 by type specific HPV testing at Week 36 visit
- 6. Proportion of subjects with no progression of cervical HSIL to cervical carcinoma from baseline on histology (i.e. biopsies or excisional treatment) at Week 36 visit
- 7. Proportion of subjects who have cleared HPV-16 and/or HPV-18 on specimens from non-cervical anatomic locations (oropharynx, vagina and intra-anal) at Week 36 Visit
- 8. a. Levels of serum anti-HPV-16 and anti-HPV-18 antibody concentrations at Week 15 and 36 visits
 - b. Interferon-γ ELISpot response magnitudes at baseline, Weeks 15 and 36 visits
 - c. Flow Cytometry response magnitudes at baseline and Week 15 visits

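### The between-arm ELISA comparison leaves out baseline titer, although secondary objective 8 asks for the humoral response relative to baseline

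*SAP*

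**What the plan says.** SAP section 2.2, item 8, sets the aim: "Determine the humoral and cellular immune response following administration of VGX-3100 compared with placebo", assessed "at post dose 3 and Week 36 visits as assessed relative to baseline". One qualifier covers both kinds of response.

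Section 3.2.2, item 8, gives the endpoints:
- 8a (antibody): "Levels of serum anti-HPV-16 and anti-HPV-18 antibody concentrations at Week 15 and 36 visits"
- 8b: "ELISpot response magnitudes at baseline, Weeks 15 and 36 visits"
- 8c: "Flow Cytometry response magnitudes at baseline and Week 15 visits"

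Baseline is named in 8b and 8c but not in 8a.

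Section 8.3 states that sera are collected and assessed at baseline, Week 15 and Week 36, and that every endpoint is summarised at each visit. For the between-arm comparison it splits the assays. The cellular ones enter as "Increases from baseline for each post baseline visit from ELISpot and Flow Cytometry", while for the humoral one "titers for each post baseline visit from ELISA will be compared between treatment arms". All are analysed as a difference in medians with an exact non-parametric 95% interval and no covariate. The population is the mITT set with at least one immunogenicity measurement.

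No reason is given for treating ELISA differently. Section 11, which lists changes from the protocol, does not mention it.

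**The concern.** ELISA is the only humoral measure in the plan. If its between-arm contrast ignores baseline, the humoral half of objective 8 is compared with placebo in a form other than the one the objective states. The cellular half is compared as stated.

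The SAP uses baseline in its other continuous between-arm comparisons where a baseline value exists. Section 8.4 compares tissue markers, SF-36 and EQ-5D-5L as changes from baseline.

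Baseline titer could plausibly vary between women here. Every subject enters positive for HPV-16, HPV-18 or both (section 3.1), and prior prophylactic HPV vaccination is common enough to be planned as a subgroup (section 8). If baseline titer predicts later titer, an unadjusted comparison carries that variation into the width of its interval. What is at stake is agreement between objective and analysis, and possibly some precision, for one secondary endpoint.

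**Working it through.** **Step 1. Set the three places side by side.**

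| Assay | Objective 8 | Endpoint | Between-arm variable in 8.3 |
|---|---|---|---|
| ELISA (humoral) | relative to baseline | 8a: Weeks 15 and 36 | post-baseline titer |
| ELISpot (cellular) | relative to baseline | 8b: baseline, Weeks 15 and 36 | increase from baseline |
| Flow cytometry (cellular) | relative to baseline | 8c: baseline, Week 15 | increase from baseline |

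The two cellular rows agree across all columns. In the ELISA row the endpoint and the analysis agree with each other, but neither agrees with the objective.

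**Step 2. Are the data there?** Yes. Section 8.3 lists baseline among the serum time points, and footnote f of the schedule of events requires at least 16 ml of serum in total before dosing on Day 0.

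**Step 3. Is there a plan figure to reproduce?** Not for this point: the SAP gives no titer variance, correlation or precision target. Its one design figure (198 subjects, 2:1, 90% power for 35% versus 14%) belongs to the primary endpoint. It reproduces, with 66 + 132 = 198 and power 90.3%, and nothing here depends on it.

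**Step 4. Illustrate the precision at issue.** Let r be the within-arm correlation of baseline and post-baseline log titer, with equal variances. The values of r are assumed. Relative to the variance of the arm difference using post-baseline titer only:
- baseline-adjusted linear model: 1 − r²
- change from baseline: 2(1 − r)

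| Assumed r | Adjusted: 1 − r² | Interval width, √(1 − r²) | Change: 2(1 − r) |
|---|---|---|---|
| 0.3 | 1 − 0.09 = 0.91 | 0.954 (5% narrower) | 1.4 |
| 0.5 | 1 − 0.25 = 0.75 | 0.866 (13% narrower) | 1.0 |
| 0.7 | 1 − 0.49 = 0.51 | 0.714 (29% narrower) | 0.6 |

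At r = 0 the adjusted ratio is 1, so nothing is gained. The change score beats the post-baseline comparison only when 2(1 − r) < 1, that is, when r > 0.5.

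**Step 5. Check with an estimate closer to the planned one.** A simulation of 132 versus 66 subjects with normal log titers and no treatment effect used the median of all pairwise differences between arms. The variance of change relative to post-baseline only was 1.43, 0.98 and 0.55 at r = 0.3, 0.5 and 0.7, close to the formula. Mean error was about zero for both, so neither is biased. The simulation did not cover the baseline-adjusted model.

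**The case against.** The strongest reply is that the choice looks deliberate and is valid. Endpoint 8a and section 8.3 make the same split between ELISA and the cellular assays, and a comparison of post-baseline titers between randomized arms is unbiased. Any chance imbalance at baseline is sampling error that the interval already reflects. This stands. A reader might infer that the planned ELISA result would be biased or invalid; the documents do not support that.

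A reader might also infer that baseline titers go unused, or that the humoral objective is left wholly unanswered. That too goes too far. Section 8.3 summarises every endpoint at each visit, and section 4.4 displays summaries by arm, so baseline titers will be visible. Baseline is absent only from the between-arm contrast.

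The precision argument is conditional. No correlation is given, the 1 − r² formula belongs to a linear model on log titer, and it does not carry over directly to a difference in medians. The percentages in the working are therefore illustrations, not a measured loss.

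Finally, copying the cellular method would not be a clear gain, since simple change from baseline is less precise than the planned comparison when r is below 0.5. This also stands, and it is why the remedy adds an analysis and does not swap one for another.

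None of this removes the mismatch with objective 8, for which the SAP gives no reason.

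**Conclusion.** The point holds as a mismatch between the objective and the analysis, with a possible but unquantified loss of precision. Objective 8 calls for a humoral comparison with placebo relative to baseline; endpoint 8a and section 8.3 supply one on post-baseline titers only.

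Under a linear model on log titer with equal variances, adjustment would cut the variance to 0.91, 0.75 or 0.51 of the unadjusted value at assumed r of 0.3, 0.5 or 0.7. If r is near zero the gain vanishes, and what remains is the agreement of the three sections.

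The consequence is modest. This is a secondary endpoint reported with intervals and no planned p-value. The primary test and the sample size are unaffected, and immunogenicity is not among the Week 36 unblinded summaries listed in section 10. The change is worth making because it is cheap and the baseline sera are already collected.

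**What to change.** 1. Keep the planned comparison of ELISA titers at Weeks 15 and 36.
2. Add to section 8.3 a between-arm comparison of log titer at each of these visits, for anti-HPV-16 and anti-HPV-18 separately, with baseline log titer as a covariate and a 95% interval.
3. Show fold-rise from baseline by arm, compared with the same exact non-parametric 95% interval. Do not let it replace the planned comparison, because it adds variance when r is below 0.5.
4. Amend endpoint 8a to name baseline, so that objective 8, endpoint 8a and section 8.3 agree.

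The cost is one extra model, run for two antigens at two visits, and one extra table, with no new sampling. The population requires only one immunogenicity measurement, so some subjects may have no baseline titer. They drop out of the baseline-adjusted and fold-rise comparisons but stay in the planned one; state this and report the number in each. The log scale also needs a rule, fixed before unblinding, for titers below the assay's detection limit.

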8.4. Exploratory Analysis

The relationship between the histologic regression of cervical HSIL with virologic clearance at Week 36 visit (Y/N) and a) miRNA results, b) DNA methylation results, c) colposcopy results, d) cytology results, e) HPV results, and f) baseline immunoscore results (tissue-based score derived using immunologic markers) will be examined using separate logistic regression models for each result, with histologic regression of cervical HSIL with virologic clearance as the response variable, and each of the results and treatment arm as regressor variables. Odds Ratios (ORs) and corresponding 95% CIs will be provided for the regressor variables.

Durability, as measured by clearance of HPV-16 and/or HPV-18 infection at Week 62 and 88, will be summarized by number and percentage of subjects with no evidence of HPV-16 and/or HPV-18 by treatment arm at each visit. Specifically, the virology results at Week 62 are those between Day 420 and Day 448, and the virology results at Week 88 are those between Day 602 and Day 630.

Assessment of markers including but not limited to CD8+ and FoxP3+ infiltrating cells, and visualization of Granulysin, Perforin, CD137, CD103 and PD-L1 in cervical tissue may be performed. Markers listed here may change as new relevant information becomes available. These tissue response magnitudes will be compared between treatment arms using a difference in means and associated t-distribution based 95% CIs for changes from baseline at each post-baseline time point.

Patient-Reported Outcomes

Subjects enrolled in US, Canada, Mexico, Germany and UK will complete Patient-reported outcome (PRO) questionnaires (SF-36, EQ-5D-5L, and two additional Global PRO questions assessing quality of life after excision or biopsy). Either SF-36 or EQ-5D-5L or both instruments will be completed at baseline, Weeks 4, and Week 12, 8-14 days following each dose, 8-14 days post Week 28, Week 36, 8-14 days post Week 40 and

Week 88. The two additional Global PRO questions assessing quality of life after excision or biopsy will be completed at Week 40.

For the SF-36, section scores at each of the eight domains (Physical functioning, Role limitations due to physical problems, Bodily pain, General health, Vitality, Social functioning, Role limitations due to emotional problems, and Mental health) and score change from baseline will be summarized at each visit by treatment arm. Scoring of the eight SF-36 subscales will be done by QualityMetric Health Outcomes(tm) Scoring Software 5.0.

For the EQ-5D-5L, each of the five domains (Mobility, Self-care, Usual activity, Pain/discomfort, Anxiety/depression) and Global Health Status Score will be summarized at each visit and relative to baseline by treatment arm.

For the two additional Global PRO questions assessing quality of life after excision or biopsy, the time outcome and the binary outcomes to Y/N question will be summarized by treatment arm.

SF-36 scores will be compared between treatment arms using exact non-parametric 95% confidence intervals for the differences in median changes from baseline. The EQ-5D-5L scores will be analyzed in the same fashion. Days of worsened quality of life for the Week 40 Quality of Life questionnaire will be analyzed using an exact non-parametric 95% confidence interval for the difference in the median number of days. The Y/N worsened quality of life response for the Week 40 Quality of Life questionnaire will be analyzed using a 95% Miettinen and Nurminen confidence interval for the difference in proportions between treatment arms.

In addition, PRO endpoints at each visit that occurs after Week 36 will be summarized according to those with excision (excluding biopsy) versus those without.

The mITT population with at least one post baseline corresponding measurement will be used for PRO analyses.

9. Safety Analysis

All safety summaries and analyses will be based on all subjects in the safety analysis set.

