2.3. Exploratory Objective

The exploratory objectives of this study are:

- 1. Evaluate tissue immune responses to VGX-3100 in cervical samples
- 2. Describe association of microRNA (miRNA) profile, DNA methylation profile, previous colposcopy, cytology and HPV testing results with Week 36 histologic regression
- 3. Describe the durability of virologic clearance of HPV-16 and/or HPV-18 for subjects treated with VGX-3100 compared with those treated with placebo
- 4. Describe the patient-reported outcomes (PRO) for subjects treated with VGX-3100
- 5. Determine whether a tissue-based score derived using an immunologic markers (Immunoscore) at baseline is predictive for histological and virological response to VGX-3100 at Week 36

3. Investigational Plan

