3.2.3. Exploratory Endpoints

The exploratory endpoints of this study are:

- 1. Assessment of markers including but not limited to CD8+ and FoxP3+ infiltrating cells. Additional assessments may include visualization of Granulysin, Perforin, CD137, CD103 and PD-L1 in cervical tissue as sample allows. Markers listed here may change as new relevant information becomes available
- 2. Colposcopy, cytology, and HPV test results (Weeks 8, 15 and 28 visits), miRNA profile (baseline, Week 8) and DNA methylation profile (baseline, Week 15) in conjunction with histologic regression of cervical HSIL at Week 36 visit
- 3. Proportion of subjects with no evidence of HPV-16 and/or HPV-18 by type specific HPV testing at Weeks 62 and 88 visits
- 4. Patient-reported outcome questionnaires self-administered at baseline, after each dose at Weeks 4, 12, 8-14 days following each dose, and at Weeks 28, 36, 40 and 88 by subjects enrolled in US, Canada, Mexico, Germany and UK
- 5. Immunoscore results for VGX-3100 treated subjects and in conjunction with histological and virological outcomes at Week 36

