4.1. Sample Size

A total of 198 subjects will be randomized to receive either 6 mg VGX-3100 or placebo IM followed by EP in a 2:1 ratio. This sample size provides 90% power to declare VGX-3100 superior to placebo, assuming the true proportion of subjects who achieve the primary endpoints is 35% and 14% for VGX-3100 and placebo, respectively. These proportions also incorporate missing data (~10%) classified as non-regressors (failures). The assumptions are based on the Phase 2 study results.

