4.2. Randomization, Stratification, and Blinding

Subjects will be randomized (2 VGX-3100:1 Placebo) in a stratified manner according to a) the degree of CIN observed in the biopsy specimens at screening (CIN2 vs. CIN3), b) Body Mass Index (BMI) category (≤25 vs. >25 kg/m2) on Day 0 visit, and c) age category (<25 years vs. ≥25 years) on Day 0 visit. There will be no pre-determined number of subjects required to be randomized within each stratum. To ensure that milder CIN2 disease is not over-represented in the study, the percentage of subjects enrolled with CIN2 will not exceed 50% of the total enrolled.

The study is double-blinded to both investigators and subjects.

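### The exploratory logistic models in SAP 8.4 do not match their objectives: a composite response where objective 2 names histologic regression, and a pooled Immunoscore effect where endpoint 5 concerns the VGX-3100 arm

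*SAP*

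**What the plan says.** Section 8.4 of the SAP plans a separate logistic regression for each of six sets of results: a) miRNA, b) DNA methylation, c) colposcopy, d) cytology, e) HPV and f) baseline Immunoscore. Every model is fitted "with histologic regression of cervical HSIL with virologic clearance as the response variable, and each of the results and treatment arm as regressor variables". The output of each model is an odds ratio with 95% confidence interval per regressor. No histology-only model, no marker-by-arm term and no model within one arm is planned.

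The aims behind these models are worded differently:

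- Exploratory objective 2 (section 2.3) asks for the association of miRNA, methylation, "previous colposcopy, cytology and HPV testing results with Week 36 histologic regression".
- Exploratory endpoint 2 (section 3.2.3) places the same markers, including HPV tests at Weeks 8, 15 and 28, "in conjunction with histologic regression of cervical HSIL at Week 36 visit".
- Exploratory objective 5 (section 2.3) asks whether Immunoscore "at baseline is predictive for histological and virological response to VGX-3100 at Week 36". Endpoint 5 (section 3.2.3) restricts this to subjects treated with VGX-3100.

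Section 11, which lists changes from the protocol, mentions neither difference. A histology-only responder is already defined in the first row of Table 2, for secondary endpoint 2.

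**The concern.** There are two mismatches inside the one document.

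**Response variable, items a) to e).** A marker can be associated with the composite through regression, through viral clearance, or through both. Objective 2 asks only about the first. HPV results are the most exposed: an earlier HPV test is expected to relate to the Week 36 HPV test, which is one of the two components of the response. An odds ratio well above 1 could then be read as evidence that HPV testing anticipates lesion regression when it carries no such information. In the other direction, a marker that does relate to regression is diluted.

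**Pooling over arms, item f).** With score and arm as main effects only, the model assumes one Immunoscore odds ratio for both arms. If the effect differs by arm, the estimate is a mixture, and it is not the VGX-3100 quantity that endpoint 5 describes. Nor can it separate a marker of response to VGX-3100 from one that is prognostic in either arm.

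**Working it through.** **Inputs from the SAP.** Section 4.1: "A total of 198 subjects will be randomized". Section 4.2: 2:1 allocation, so 132 VGX-3100 and 66 placebo. Section 4.1 also gives the rates, "assuming the true proportion of subjects who achieve the primary endpoints is 35% and 14% for VGX-3100 and placebo, respectively".

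**The plan's own figure.** For 35% against 14%, 2:1, one-sided 0.025 and 90% power, the normal-approximation formula with pooled variance and no continuity correction gives 66 + 132 = 198 (power 90.3%). The stated size reproduces. Nothing below changes it.

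**Expected composite responders.** 132 × 0.35 = 46.2 and 66 × 0.14 = 9.2. The pooled rate is 55.4/198 = 28%.

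**Objective 2, HPV results.** The SAP gives no regression rate, clearance rate or HPV test agreement, so these are assumptions.

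- Histologic regression is 50%, independent of clearance and of the Week 28 HPV test. The true histologic odds ratio is therefore 1.
- Week 36 HPV-negative is 0.28/0.50 = 56%, which matches the pooled composite rate.
- Let s be the probability of a negative Week 28 test in those negative at Week 36, and f the same in those positive at Week 36.

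Composite rate if Week 28 negative: 0.5 × 0.56s / (0.56s + 0.44f).
Composite rate if Week 28 positive: 0.5 × 0.56(1−s) / (0.56(1−s) + 0.44(1−f)).

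| s, f | Rate if negative | Rate if positive | Composite OR |
|---|---|---|---|
| 0.65, 0.20 | 0.5 × 0.364/0.452 = 0.403 | 0.5 × 0.196/0.548 = 0.179 | 3.1 |
| 0.75, 0.15 | 0.5 × 0.420/0.486 = 0.432 | 0.5 × 0.140/0.514 = 0.136 | 4.8 |
| 0.85, 0.10 | 0.5 × 0.476/0.520 = 0.458 | 0.5 × 0.084/0.480 = 0.088 | 8.8 |

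This table leaves out treatment arm, which the planned model includes. Keep 50% regression in both arms and set clearance to 0.35/0.50 = 70% and 0.14/0.50 = 28%. The same formulas then give 2.3, 3.3 and 5.6 within VGX-3100 and 4.9, 9.1 and 19.8 within placebo. The additive model with arm, fitted to these expected counts, gives 2.7, 4.2 and 7.5. Adjusting for arm lowers the values somewhat and leaves the conclusion unchanged.

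**Objective 2, dilution.** Assume a binary marker with 50% prevalence and a true histologic odds ratio of 3, in the VGX-3100 arm with 50% regression and 70% clearance among regressors. Regression is 0.366 and 0.634 by marker. The composite is 0.7 times these, 0.256 and 0.444, so the odds ratio is (0.444/0.556)/(0.256/0.744) = 2.3. Over regression rates of 45 to 55%, with the composite held at 35%, it is 2.1 to 2.5.

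**Objective 5, Immunoscore.** Again assume a binary marker with 50% prevalence, and fit the additive model to expected counts at 132/66 and 35%/14%.

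| True OR, VGX-3100 | True OR, placebo | Pooled OR |
|---|---|---|
| 3 | 3 | 3.0 |
| 3 | 1 | 2.37 |
| 1 | 3 | 1.24 |

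A hand check weights the log odds ratios by n·p·(1−p): 132 × 0.35 × 0.65 = 30.0 and 66 × 0.14 × 0.86 = 7.9. For 3 and 1 this gives exp(30.0 × ln 3 / 38.0) = 2.38.

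**Precision of the two remedies** (true odds ratios 3 and 1). With marker-specific rates of 0.229 and 0.471 in VGX-3100 and 0.14 in placebo:

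- Within VGX-3100, SE² = 1/(66 × 0.229 × 0.771) + 1/(66 × 0.471 × 0.529) = 0.147, so SE = 0.38. An odds ratio of 3 would have a 95% CI of about 1.4 to 6.4.
- For the interaction, add 2/(33 × 0.14 × 0.86) = 0.503. SE = √0.650 = 0.81, and power is 28% for a ratio of odds ratios of 3.

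**The case against.** The strongest reply is that these are exploratory analyses reported as odds ratios with intervals. Objective 2 only asks to describe an association, and section 8.4 names its response variable openly, so a result reported as specified would not claim lesion regression alone. The composite contains histologic regression and is related to the question. All of this stands, and it limits the weight of the point. It does not remove the mismatch: the objective and the endpoint both name regression, and no planned model estimates that association.

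Four stronger readings are tempting and are not supported.

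- A reader might infer that the models cannot answer either question. That goes too far. The composite gives a diluted but related association, and the pooled Immunoscore odds ratio is right when the marker effect is equal in both arms.
- A reader might call the HPV model circular. It is not. A test at Week 8, 15 or 28 is a different sample from the Week 36 test, so this is prediction from an earlier measurement. The difficulty is only that part of what is predicted is virology, which objective 2 does not ask about.
- A reader might quote larger odds ratios. With 30 to 40% HPV-negative at Week 36 and the same 50% independent regression, the unadjusted calculation gives about 4 to 19. Those inputs imply a composite rate of 15 to 20%, below the 28% that follows from section 4.1.
- A reader might infer that an interaction term is required. Objective 5 need not use predictive in the technical sense opposed to prognostic, and endpoint 5 concerns VGX-3100 treated subjects, which a model within that arm addresses. With about 9 expected placebo responders the interaction would rarely settle the question.

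Nor does section 8.4 say that the treatment-arm odds ratio from these models will be presented as a treatment effect, so no point is made of it.

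**Conclusion.** The point holds in limited form. For items a) to e), the response variable contradicts objective 2 and endpoint 2. The resulting association is distorted, most of all for HPV results: about 3 to 9 where the histologic odds ratio is 1, or 2.7 to 7.5 once arm is in the model. These sizes rest on assumed regression, independence and HPV test agreement. The direction needs only that an earlier negative HPV test makes Week 36 clearance more likely among regressors.

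For item f), the composite suits objective 5, whose response is both histological and virological. The mismatch is the pooling over arms, which recovers the VGX-3100 odds ratio only under equal marker effects. The values 2.37 and 1.24 rest on an assumed marker prevalence of 50% and assumed arm-specific odds ratios.

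With the protocol not at hand, it is unknown which outcome it specifies for these models; the contradiction is within the SAP. The impact is confined to exploratory results. Sample size, type I error and the primary and secondary analyses are untouched.

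**What to change.** - **Items a) to e):** in section 8.4, make the Table 2 histology-only responder (secondary endpoint 2) the response variable. Keep the composite as an additional model if wanted, labelled as such.
- **Item f):** keep the composite and fit the model within the VGX-3100 arm. Alternatively, add a score-by-arm term and report the odds ratio with its confidence interval in each arm, stated in advance to be descriptive.

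The cost is a few lines of SAP text and a few model statements. No new data, derivations or subjects are needed. The price of the within-arm model is that it uses 132 subjects and about 46 expected responders rather than 198 and about 55. The price of the interaction is an imprecise estimate.

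### The Section 8.4 marker models leave out baseline CIN grade, so their odds ratios cannot show whether a baseline marker, above all the Immunoscore, adds anything to grade

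*SAP*

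**What the plan says.** SAP Section 8.4 relates the Week 36 response to six kinds of result: miRNA, DNA methylation, colposcopy, cytology, HPV and the baseline Immunoscore. The relationship "will be examined using separate logistic regression models for each result". The outcome in every model is the composite of regression and clearance, and the predictors are "each of the results and treatment arm as regressor variables". The output is stated as "Odds Ratios (ORs) and corresponding 95% CIs will be provided for the regressor variables". No baseline covariate enters, and no adjusted version is planned elsewhere.

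Section 4.2 stratifies randomisation on screening CIN grade (CIN2 or CIN3), BMI category and age category. It also caps the CIN2 share at half of those enrolled, and gives the reason as "To ensure that milder CIN2 disease is not over-represented in the study".

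Section 2.3 gives the aims. Objective 2 is to describe how the miRNA, methylation, colposcopy, cytology and HPV results are associated with regression. Objective 5 asks whether the baseline Immunoscore "is predictive for histological and virological response to VGX-3100 at Week 36".

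**The concern.** Stratified randomisation balances CIN grade between the arms. It does not balance grade between marker-high and marker-low subjects, because markers are not randomised. The Immunoscore is a tissue-based baseline score, and the screening cervical tissue is also what is graded CIN2 or CIN3, so a link between score and grade is plausible. By calling CIN2 milder, stratifying on grade and capping CIN2, the SAP allows that grade may matter for outcome.

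If grade is related to both marker and response, the marker OR from the planned model combines the marker's own association with that of grade. An OR away from 1 could then arise with no marker association within CIN2 or within CIN3. At stake is how an exploratory result is read, chiefly the answer to objective 5. The primary analysis and the sample size are untouched.

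**Working it through.** **The plan's own figure.** The SAP states no figure for the marker models. Its sample size (Section 4.1) reproduces: 35% against 14%, 2:1 allocation, one-sided 0.025, pooled variance and no continuity correction give 132 + 66 = 198 subjects with 90.3% power. Expected responders at these rates are 0.35 × 132 + 0.14 × 66 = 46.2 + 9.2 = 55.4.

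**Hand illustration.** None of the following inputs is in the SAP; all are assumed.
- Half the subjects have CIN3 (the 50% cap on CIN2 permits this).
- Response is 25% in CIN3 and 45% in CIN2, averaging 35%, the VGX-3100 planning rate. The implied grade OR is (0.45/0.55)/(0.25/0.75) = 2.45.
- The marker is high in a share s of CIN3 and 1 − s of CIN2, with no effect within grade.

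With equal numbers in each grade, a share s of marker-high subjects have CIN3, so:
- P(response | high) = s × 0.25 + (1 − s) × 0.45
- P(response | low) = (1 − s) × 0.25 + s × 0.45

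| s | High | Low | Crude OR |
|---|---|---|---|
| 0.6 | 0.33 | 0.37 | (0.33/0.67)/(0.37/0.63) = 0.84 |
| 0.7 | 0.31 | 0.39 | (0.31/0.69)/(0.39/0.61) = 0.70 |
| 0.8 | 0.29 | 0.41 | (0.29/0.71)/(0.41/0.59) = 0.59 |

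The within-grade OR is 1 in every row. If response is the same in both grades, the two probabilities are equal and the crude OR is 1.

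**Simulation at the trial's size.** Each run has 198 subjects (132:66) with overall response of 35% and 14%. A binary marker agrees with grade with a set probability and has no effect of its own. There were 1,500 runs per setting, of which at most 3 could not be fitted. Here marker-high goes with CIN2, so spurious ORs lie above 1. The table uses a CIN2 share of 50% and marker-grade agreement of 80%.

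| Assumed grade OR | Planned model: median OR | 95% CI excludes 1 | Grade added: median OR | 95% CI excludes 1 |
|---|---|---|---|---|
| 1 | 1.00 | 4.9% | 0.99 | 4.9% |
| 1.5 | 1.29 | 10.7% | 0.98 | 5.2% |
| 2 | 1.48 | 23.2% | 0.98 | 5.5% |
| 3 | 1.90 | 48.5% | 0.99 | 4.8% |

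Over agreement of 70% to 90%, a CIN2 share of 30% or 50% and a grade OR of 1.5 to 3, the planned model gives a median OR of 1.17 to 2.37. Its CI excludes 1 in 6.5% to 72.6% of runs. Across all settings, including a grade OR of 1, adding grade gives a median OR of 0.95 to 1.02, and the CI excludes 1 in 3.5% to 5.7% of runs.

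**The case against.** The strongest objection is that the planned OR answers the question the SAP asks. Objective 2 is to describe association. A marker that tracks grade, where grade affects response, is truly associated with response. Neither objective 2 nor objective 5 says the marker must add to the screening biopsy. This stands: the planned model is a valid description of marginal association, and grade confounds it only for the further question of whether the marker contributes beyond grade.

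Three other points also stand.
- The SAP gives no response rate by grade, so every input to the illustration is assumed. Section 8.1 will show responder proportions by stratification factor, which reveals whether grade matters. It does not cross grade with any marker, so it cannot replace an adjusted OR.
- Section 3.2.3 places colposcopy, cytology and HPV results at Weeks 8, 15 and 28, and miRNA and methylation partly after dosing. Post-dose results may reflect response already under way, so the illustration fits the baseline markers only.
- Nothing in the SAP links age or BMI category to a marker or to response beyond their use as stratification factors.

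A reader might go further and infer that a marker tracking CIN grade will appear to predict response. The document does not support that. It would need grade to be associated with the composite response, for which the SAP gives no figure. Even at an assumed grade OR of 2 with 80% agreement, the interval excludes 1 in only about 23% of runs.

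**Conclusion.** The point holds as a limit on interpretation, not as an error in the planned model. A marker-plus-arm OR cannot separate a baseline marker from CIN grade, and this matters most for the Immunoscore under objective 5. The size is unknown. It runs from none, if grade is unrelated to response, to a crude OR of 0.84 to 0.59 under the assumed 25% and 45% response rates, with no marker effect within grade. These values rest on a binary marker, complete marker data and the assumed links between marker, grade and response.

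Severity is low. The analyses are exploratory and carry no test, threshold or decision rule.

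**What to change.** Keep the Section 8.4 models as the description of association. Add one sentence: for the Immunoscore and the baseline miRNA and methylation results, a supplementary OR with 95% CI will be reported beside the planned one, from the same model plus baseline CIN grade (CIN2 or CIN3). Age and BMI categories are not needed. State that the supplementary OR addresses whether the marker is associated with response within grade. A logistic OR can also shift when a prognostic covariate is added without any confounding, so a modest difference between the two should not be read as confounding in itself.

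The cost is SAP wording and one extra term per model, using data already collected. The supplementary intervals will be slightly wider. At the planning rates there are about 55 responders for an intercept, arm, grade and a single-term marker, or about 14 per parameter (55.4/4 = 13.9). Section 3.2.3 describes the Immunoscore endpoint for VGX-3100 subjects. If that analysis is limited to that arm, about 46 responders remain and the arm term drops out (46.2/3 = 15.4 per parameter). A multi-component miRNA or methylation profile would use more parameters, and missing marker data would reduce these counts.
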